3.3. Primary Objective

Reduce internalized stigma of mental illness among adult inpatients in acute care with a music therapy intervention focused on writing, recording, and releasing music to the general public for the purpose of mental health advocacy.

3.4. Primary Outcome Variables

ISMI score pre-treatment, ISMI score post-treatment

3.5. Secondary Objective

Reduce internalized stigma of mental illness across subject diagnostic categories. ISMI

scores will be compared between subjects with no diagnosis or diagnosed with schizophrenia spectrum and other psychotic disorders, bipolar and related disorders, depressive disorders, and anxiety disorders, as classified by the American Psychiatric Association's *Diagnostic and Statistical Manual of Mental Disorders* (5th ed.; DSM–5; American Psychiatric Association, 2013).

3.6. Secondary Outcome Variable

ISMI score pre-treatment, ISMI score post-treatment, ISMI score 3 weeks post-treatment, Diagnostic Category: No Diagnosis, Diagnostic Category: Schizophrenia Spectrum and Other Psychotic Disorders, Diagnostic Category: Bipolar and Related Disorders, Diagnostic Category: Depressive Disorders, and Diagnostic Category: Anxiety Disorders

3.7. Exploratory Objective

Examine the persistence of the treatment effect, to be measured at 3 weeks after completion of the treatment sequence.

3.8. Exploratory Outcome Variables

ISMI score 3 weeks post-treatment

4 - Study Design

4.1 General Design

This prospective clinical trial's pseudo cluster randomized controlled design (Borm et al., 2005) will take advantage of the unit's two separate residential areas ("wings", ACU West and ACU East) to minimize contamination and selection bias by randomizing treatment and control conditions to each wing, rather than each individual subject (see Figure 1).

[figure not shown]

Figure 1. Pseudo Cluster Randomization Procedure

Patients on the unit currently receive opportunities to take part in several groups per day focused on topics of coping skills, mindfulness, journaling, creative arts, wellness recovery, recreation, and at least one music therapy group, as part of the standard of care. The current study improves upon the standard of care by providing a protocolized intervention sequence targeted at reducing internalized stigma of mental illness.

The intervention consists of a sequence of five music therapy songwriting and recording groups, one per day. Internalized stigma will be assessed within 3 days of admission (pretest/baseline), at ten days (posttest), and at 3 weeks from baseline (follow-up), using the Internalized Stigma of Mental Illness Inventory (Ritsher et al., 2003; Appendix 2).

4.1.1 Study Duration

The proposed study duration is one year, with eight months allotted for data collection, and four months allotted for data analysis. Subjects will be involved for a period of 21 days, including follow-up data collection (See Table 4). Results of this study can help inform the feasibility of collecting follow-up data from this population, as patient adherence to aftercare plans can be unpredictable.

Day	Treatment Group	Control Group

1-3	Enrollment, Pre- Test/Baseline	Enrollment, Pre-Test
4-10	Treatment Sequence	No Treatment Sequence
8-10	Post-Test	Post-Test
21	Follow-up data collected	Follow-up data collected

Table 4. Study Timeline Per Cohort

4.1.2 Number of Study Sites

This study will take place at Hackensack Meridian Health Carrier Clinic, [name]

4.2 Study Population

All patients who are anticipated to remain admitted to the unit for at least 7 days will be considered regardless of gender or racial/ethnic background with the exception of those less than 18 years of age. Additional exclusion criteria will include S1 status (1:1 patient observation), evidence of organic brain disease, severe acute symptomatology, hearing deficit, and intellectual disability. Eligible patients must be able to read and comprehend the ISMI questionnaire, and provide informed consent as determined by their doctors.

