4.3. Study procedures

Patients will be identified and referred upon admission to the Acute Care Unit at HMH Carrier Clinic by the treatment team (attending doctors, nurses, and social workers). All subjects who are anticipated to remain admitted to the unit for at least 7 days will be considered regardless of gender or racial/ethnic background with the exception of those less than 18 years of age.

Internalized stigma will be assessed within 3 days of admission (pretest/baseline), at ten days (posttest), and at 3 weeks from baseline (follow-up), using the Internalized Stigma of Mental Illness Inventory (Ritsher et al., 2003; Appendix 2). The ISMI is a widely-used measure with acceptable internal consistency (α = .72-.90) and test–retest reliability (r = .68-.92; Boyd et al., 2014; Chang et al., 2016). It was selected over the Perceived Devaluation

and Discrimination Scale (PDD; Link, 2987) and Self-Stigma in Mental Illness Scale (SSMOI; Tucker et al., 2013) due to concerns about internal consistency and psychometric properties of these measures (Brohan et al., 2010). Data collection will include the subject's name, diagnoses, treatment ID number, and ISMI score. Treatment effect will be measured by using a two-factor, mixed-design analysis of variance (ANOVA). A P value of less than 0.05 will be considered to indicate statistical significance.

Description of Procedures

The music therapy treatment group will utilize a certified music therapist to facilitate a series of 5 group music therapy sessions over the course of 5 to 7 consecutive weekdays. Groups will be composed of 5 to 7 patients and the MT. There is no standard number of sessions for interventions addressing internalized stigma, and the available literature varies from one session in a single day to twenty sessions over a period of months. Since the average length of stay for acute care unit patients is 7 to 10 days, 5 sessions is the maximum feasible number of sessions to complete the treatment sequence for shorter stays. Though patients typically receive daily music therapy groups as part of the standard of care, this study improves upon the standard of care by providing a protocolized intervention sequence targeted at reducing internalized stigma of mental illness.

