5.7. Follow-up and end-of study

Subjects will be hospitalized for at least the first two phases of data collection (pretest and posttest). The 3 week follow-up data may be collected either post-discharge or in the hospital, as required by the subject's unique treatment needs.

Subjects will be hospitalized for at least the first two phases of data collection (pretest and posttest), which will be administered in hard copy by research staff. The 3 week follow-up data may be collected by research staff either post-discharge by phone or in person in the hospital by hard copy, as required by the subject's unique treatment needs.

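### The 7-day anticipated-stay rule has no stated starting point and, on most readings, does not reach the scheduled post-test, so some patients enter who cannot give the primary outcome on schedule

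*Combined protocol and SAP*

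**What the plan says.** **Entry.** Section 4.2 states: "All patients who are anticipated to remain admitted to the unit for at least 7 days will be considered". Section 4.3 repeats the rule and adds when patients are found: "Patients will be identified and referred upon admission to the Acute Care Unit". Section 5.1 has screening every morning. The eligibility and exclusion lists in 4.2.2 do not mention length of stay.

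**Schedule.** Section 4.1 has internalized stigma "assessed within 3 days of admission (pretest/baseline), at ten days (posttest), and at 3 weeks from baseline (follow-up"; sections 4.3 and 5.5 give the same times. Table 4 (section 4.1.1) has enrolment and pre-test on days 1-3, the treatment sequence on days 4-10, and the post-test on days 8-10 in both groups. Section 4.1 has five sessions, one per day. Section 4.3 describes "a series of 5 group music therapy sessions over the course of 5 to 7 consecutive weekdays" and places the post-test after the fifth session.

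**Stay.** Section 4.3 reasons: "Since the average length of stay for acute care unit patients is 7 to 10 days". It presents five sessions as the most that shorter stays can accommodate. Section 5.7 says: "Subjects will be hospitalized for at least the first two phases of data collection (pretest and posttest").

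**Consequence of early discharge.** Section 5.2 drops subjects discharged during the treatment phase and collects nothing further from them. The primary outcome (3.4) needs the ISMI before and after treatment. Sections 4.2.1 and 5.8.1 accrue 50 per group and state no allowance for loss.

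**The concern.** Section 5.7 takes for granted that every subject is an inpatient at the post-test, but no entry rule secures this. The only stay rule names 7 days, and the earliest post-test day in Table 4 is day 8. With an average stay of 7 to 10 days on this unit, stays at or near the 7-day floor are to be expected.

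Two things are at stake. Some of the 50 places per group go to patients who cannot provide the primary outcome on schedule. And those who do provide it are patients who stayed longer than the criteria describe. Length of stay plausibly tracks severity and recovery, so the result would apply to a narrower population than the one stated. A better missing-data method would not remove that mismatch, because it arises at entry.

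**Working it through.** **Inputs from the documents.** Stay floor 7 days (4.2, 4.3). Sessions on days 4-10 and post-test on days 8-10 (Table 4). Post-test at ten days (4.1, 4.3, 5.5). Five sessions, one per day (4.1), on weekdays (4.3). Enrolment on days 1-3 (Table 4). Mean stay 7-10 days (4.3). The plan gives no figure for the share of patients staying to the post-test, so there is none to reproduce.

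**Step 1: when the fifth session falls.** Take admission as day 1. Session 1 is the first weekday on or after day 4, followed by four more consecutive weekdays.

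| Admitted | Mon | Tue | Wed | Thu | Fri | Sat | Sun |
|---|---|---|---|---|---|---|---|
| Fifth session on day | 10 | 10 | 10 | 9 | 8 | 10 | 10 |

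The earliest is day 8 (Friday admission, so that day 4 is a Monday). Five of the seven weekdays give day 10.

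**Step 2: 7 days counted from admission.** The stay ends on day 7. It covers the fifth session for 0 of 7 weekdays and falls short of the day 8-10 post-test window in either arm.

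**Step 3: 7 further days from screening.** Cover runs to screening day + 7.

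| Screened on | Covered to | Weekdays with fifth session covered |
|---|---|---|
| Day 1 | Day 8 | 1 of 7 (Fri) |
| Day 2 | Day 9 | 2 of 7 (Thu, Fri) |
| Day 3 | Day 10 | 7 of 7 |

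The total is 1 + 2 + 7 = 10 of 21. If the screening day itself counts as the first of the seven, cover runs to screening day + 6, and the total is 0 + 1 + 2 = 3 of 21.

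**Step 4: illustrative share leaving too early.** The documents give only the mean stay. The assumptions are a lognormal stay with mean 7, 8.5 or 10 and CV 0.4, 0.6 or 0.8, or an exponential stay with the same means; and anticipated stay equal to actual stay. With S(t) the probability of staying at least t days, the share of those staying at least 7 days who leave before day t is 1 - S(t)/S(7).

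- Lognormal: variance of log stay = ln(1 + CV²); mean of log stay = ln(mean) - ln(1 + CV²)/2.
- Exponential: the share is 1 - exp(-(t - 7)/mean). For t = 8 and mean 7 it is 1 - exp(-1/7) = 0.133; for t = 10 and mean 10 it is 1 - exp(-3/10) = 0.259.

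| Model | Leave before day 8 | Leave before day 10 |
|---|---|---|
| Lognormal | 13%-30% | 35%-69% |
| Exponential | 10%-13% | 26%-35% |
| Either | about 10%-30% | 26%-69% |

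The day 8 column is the most lenient reading of Table 4. The day 10 column takes the ten-day post-test literally.

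**The case against.** The strongest reply is that the rule can be read forward. A patient anticipated to remain for 7 days may mean 7 more days from screening, and from day 3 that reaches day 10; Table 4's treatment window is itself seven days long. This stands as a reason to say that the starting point is undefined, not that the threshold is wrong on every reading. It does not rescue the rule, because it works for every weekday only with day-3 screening, and section 4.3 has patients identified on admission.

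Second, 7 days is a floor for being considered. The treatment team also judges appropriateness (6.5), and section 5.7 shows that retention to the post-test was intended. That is fair on intent, but none of these passages makes staying to the post-test a condition of entry.

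Third, a reader might infer that the session span in 4.3 always overruns Table 4. Spread over seven weekdays from day 4, the last session would fall on days 12-14. The documents do not support leaning on this. Sessions are one per day (4.1), and five weekday sessions occupy five calendar days, or seven across a weekend, so the phrase is probably a slip for calendar days. On that reading every sequence starting on the first weekday from day 4 ends by day 10. The wording needs reconciling, no more.

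Fourth, a reader might infer a power shortfall or bias between arms. Neither is shown. The same criterion applies in both wings. In the simplest model (single measurement, f = 0.33, no clustering) about 76 subjects suffice for 80% power, and 100 reduced by 25% to 38 per arm still gives about 0.81.

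**Conclusion.** The point holds as an inconsistency between the entry rule and the schedule. On the admission count, a patient with a 7-day stay meets the rule but misses both the fifth session and the post-test window. On the most favourable forward count, the fifth session is covered in 10 of 21 combinations. This rests on the documents' own figures, with admission taken as day 1.

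It applies to patients whose stay ends at day 7 and to many whose stay ends on day 8 or 9. A reader might infer that everyone admitted under the rule is lost; patients with longer stays are unaffected. Nor is 69%, or any single percentage, an established loss rate. The ranges of about 10%-30% (day 8) and 26%-69% (day 10) depend on assumed distributions and on which post-test day is meant. They show only that the share need not be small.

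The consequence is missing primary outcomes and an analysed group that is a longer-stay subset of the stated population. The change should be made; it is cheap, and it matches what section 5.7 already assumes.

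**What to change.** State one stay requirement, with its starting point, in identical words in 4.2, 4.2.2 and 4.3 and for both wings: anticipated, at enrolment, to remain on the unit through the scheduled post-test. Describe the target population in the same terms when results are reported.

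Reconcile the ten-day post-test (4.1, 4.3, 5.5) and the weekday span in 4.3 with Table 4, so that the scheduled post-test has one meaning. How the sessions are scheduled is for the investigators to decide.

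The cost is a short amendment with IRB approval (6.2) and a smaller screening pool. Those removed are mostly patients who could not have supplied the post-test. Because the pool could shrink noticeably, the investigators should check that 100 subjects can still be accrued in the collection period, which itself reads ten months in the Summary and eight in 4.1.1.

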4.2.1. Number of Participants

Based on power analysis (power=80%, see other assumptions in section 5.8.1) and the design of the study, 50 patients will be accrued to each group (n=100).

4.2.2. Eligibility Criteria

Eligible patients include adults age 18-65 who have been admitted to the HMHCC ACU, and must be able to read and comprehend the ISMI questionnaire, provide informed consent, and have severe mental illness of prolonged duration with a significant degree of disability or social dysfunction (Ruggeri et al., 2000).

Exclusion criteria will include patients younger than 18 or older than 65, patients on S1 status (1:1 patient observation) or isolation protocol, evidence of organic brain disease, severe acute symptomatology, hearing deficit, and intellectual disability.

4.2.3. Vulnerable populations

Patients on medical isolation protocol (such as those who test positive for COVID-19 while hospitalized) and patients that are unable to provide their own consent will be excluded from the study.

4.2.4. Withdrawal criteria

Subjects may withdraw from the study at any time by stating their wish to withdraw to research staff. No new data will be collected from withdrawn subjects. However, all data that have already been collected for study purposes will remain.

4.3. Study procedures

Patients will be identified and referred upon admission to the Acute Care Unit at HMH Carrier Clinic by the treatment team (attending doctors, nurses, and social workers). All subjects who are anticipated to remain admitted to the unit for at least 7 days will be considered regardless of gender or racial/ethnic background with the exception of those less than 18 years of age.

Internalized stigma will be assessed within 3 days of admission (pretest/baseline), at ten days (posttest), and at 3 weeks from baseline (follow-up), using the Internalized Stigma of Mental Illness Inventory (Ritsher et al., 2003; Appendix 2). The ISMI is a widely-used measure with acceptable internal consistency (α = .72-.90) and test–retest reliability (r = .68-.92; Boyd et al., 2014; Chang et al., 2016). It was selected over the Perceived Devaluation

and Discrimination Scale (PDD; Link, 2987) and Self-Stigma in Mental Illness Scale (SSMOI; Tucker et al., 2013) due to concerns about internal consistency and psychometric properties of these measures (Brohan et al., 2010). Data collection will include the subject's name, diagnoses, treatment ID number, and ISMI score. Treatment effect will be measured by using a two-factor, mixed-design analysis of variance (ANOVA). A P value of less than 0.05 will be considered to indicate statistical significance.

Description of Procedures

The music therapy treatment group will utilize a certified music therapist to facilitate a series of 5 group music therapy sessions over the course of 5 to 7 consecutive weekdays. Groups will be composed of 5 to 7 patients and the MT. There is no standard number of sessions for interventions addressing internalized stigma, and the available literature varies from one session in a single day to twenty sessions over a period of months. Since the average length of stay for acute care unit patients is 7 to 10 days, 5 sessions is the maximum feasible number of sessions to complete the treatment sequence for shorter stays. Though patients typically receive daily music therapy groups as part of the standard of care, this study improves upon the standard of care by providing a protocolized intervention sequence targeted at reducing internalized stigma of mental illness.

After enrollment and consent, research staff will administer the ISMI in hard copy to establish a pretest baseline. After the treatment sequence of 5 group music therapy sessions, research staff will administer the ISMI in hard copy for post-test data. The ISMI will be administered by phone or in person by research staff for 3-week follow-up data.

4.3.1. Study discontinuation

Subjects may stop taking part in this research study at any time without any penalty. If a participant withdraws from the study, no new data about them will be collected for study purposes. All data that have already been collected for study purposes will remain. This will not affect their ability to receive care at any HMH hospitals or to receive any benefits to which they are otherwise entitled.

4.4. Risks and Benefits

There are no perceived medical risks to subjects in this music therapy study. Potential benefits related to music therapy in this population include improving functioning and quality of life, and reducing depressive and anxiety symptoms. The primary potential benefit for this study is reduced internalized stigma of mental illness, with secondary potential benefits of improving symptoms associated with internalized stigma described above

The potential for loss of private information always exists; there will be procedures in place to minimize this risk (see below).

5 - Methods

5.1. Screening

Patients will be screened for eligibility each morning during the treatment team meeting. See section 6.5 ("Informed Consent") for more information.

5.2. Recruitment, enrollment and retention (including screen failures as applicable)

The consent process will take place in a private room in the acute care unit and will be overseen by [name], MT-BC, the principal investigator. The process will take 15 to 20 minutes, during which time research staff will orient the participant to the study and go over the study protocols in detail as indicated in the consent form, making sure that participant understands its content. Potential participants will be provided with the opportunity to ask any questions or take the consent form to their room and make a decision later. The participant will sign the informed consent upon complete understanding of its content and agreement on participation in the study.

Subjects who are discharged or noncompliant during the treatment phase will be dropped from the study, and no further data will be collected from these subjects. Data that has been collected will remain.

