Though a rich precedent exists for utilizing recording technology in music therapy, its clinical potential and therapeutic relevance have not been systematically investigated. Kirkland & Nesbitt (2019) offer a model of therapy-oriented recording as a medium for self-reflection and personal narrative review for patients with concurrent psychiatric disorders. When framed as a mental health advocacy project to be released to the general public, recording the patient-composed song in the MTAR treatment sequence offers patients an opportunity to proactively work together in a socially supportive context to change public perception of mental illness, to refute self-relevance of stereotypes by strengthening and broadening self-concept, and empower themselves and each other with creative, expressive tools to confront and adapt to the "experience, perception, or anticipation of negative social reactions" (Livingston & Boyd, 2010) to mental illness that initiate stigma internalization.

In this study, subjects will work together with a certified music therapist (MT) in groups of 5 to 7 subjects per group to compose, rehearse, and record a song to be released to the general public for the purpose of generating anti-stigma mental health awareness. The primary objective is to reduce internalized stigma from baseline relative to the control group as measured by the 29-item Internalized Stigma of Mental Illness Inventory (ISMI; Ritsher et al., 2003). The secondary objective, examining the association between treatment effect and diagnostic category, can assist in generating hypotheses related to effective implementation. The exploratory goal of the study is to examine the potential for the treatment effect of the music therapy intervention to persist after 21 days from baseline.

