5.8.2. Statistical Analysis Plan

Primary Analysis

Treatment effect on the primary dependent variable (ISMI score) will be measured by using a two-factor repeated-measures analysis of variance (ANOVA). A P value of less than 0.05 will be considered to indicate statistical significance.

Secondary Analysis

Treatment effect on the secondary dependent variables (diagnosis category) will be measured by using a two-factor repeated-measures analysis of variance (ANOVA). A P value of less than 0.05 will be considered to indicate statistical significance.

Exploratory Analysis

Treatment effect on the exploratory variable (ISMI score 3 weeks after baseline) will be measured by using a two-factor repeated-measures analysis of variance (ANOVA). A P value of less than 0.05 will be considered to indicate statistical significance.

6 - Trial Administration

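### Patients discharged early or judged noncompliant are dropped and not measured again, so the primary pre/post ANOVA is in effect a completers' analysis after allocation

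*Combined protocol and SAP*

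**What the plan says.** - **Drop rule (section 5.2).** "Subjects who are discharged or noncompliant during the treatment phase will be dropped from the study, and no further data will be collected". The sentence after it keeps data already collected, which for a patient dropped before the post-test means the baseline ISMI and diagnosis. *Noncompliant* is not defined.
- **Allocation (section 4.1, repeated in 5.4).** The design works "by randomizing treatment and control conditions to each wing, rather than each individual subject", so the drop rule acts after allocation.
- **Primary outcome and analysis (sections 3.4 and 5.8.2).** The outcome is ISMI before and after treatment. The analysis is one sentence, "Treatment effect on the primary dependent variable (ISMI score) will be measured by using a two-factor repeated-measures analysis of variance (ANOVA"), with significance at P < 0.05. No analysis population, missing-data method or sensitivity analysis appears there or elsewhere.
- **Control arm (section 4.1.1, Table 4).** On Days 4-10 control has "No Treatment Sequence". It does have routine care; section 4.1 says "Patients on the unit currently receive opportunities to take part in several groups per day".
- **Exposure to early discharge.** Entry requires an anticipated stay of at least 7 days (4.2, 4.3). The stated average stay is 7 to 10 days (4.3). The post-test is on Days 8-10 (Table 4) or at ten days (4.1, 4.3, 5.5). Section 5.7 expects subjects to be in hospital through the post-test.
- **Measurement after discharge (4.3, 5.7).** Phone administration is already planned for the 3-week ISMI, but not for the post-test.
- **Sample size (5.8.1).** 50 per arm, with no allowance for loss among the listed assumptions.

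**The concern.** Wing allocation defines who is to be compared. Section 5.2 then removes some of those patients for events that occur during treatment and stops measuring them. What remains is a comparison of patients who stayed and, in the MTAR arm, perhaps only of those who attended.

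Discharge can remove patients in both arms. Noncompliance depends on a definition that the protocol does not give. If it means missing study sessions, it can arise only in the MTAR arm. If it means refusing assessments or routine ward groups, it can arise in both. The documents do not say who judges it; under section 5.6 the principal investigator both delivers the intervention and administers the questionnaire. Selection that differs by arm is therefore possible but not established.

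If dropped MTAR patients change less favourably than those retained, the analysis flatters MTAR. If they change more favourably, it works against MTAR. The change in the dropped patients would never be observed, so the data could not settle which.

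**Working it through.** **1. Is it a completers' analysis?** The plan does not use the term, so this is an inference. A conventional repeated-measures ANOVA on two time points needs both scores. A patient with baseline only contributes nothing to the group-by-time test. The inference follows.

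**2. The plan's own figure.** Section 5.8.1 gives 100 patients for 80% power at f = 0.33 and alpha 0.05. A two-group F test with noncentrality N × f² needs 75, and 100 gives 90.4% power. The figure of 100 would match an unstated 25% loss, 75/(1 − 0.25) = 100, but the section does not specify the effect tested, the correlation or any loss. The calculation is under-specified rather than shown to be wrong, and the point here does not depend on it.

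**3. Bias.** The documents give no loss rate or shift, so all inputs are assumptions. Let q be the fraction of MTAR patients dropped and D the difference in mean change between dropped and retained MTAR patients, in SDs of change. The mean change of the whole arm is the retained mean plus q × D, so leaving out the dropped patients shifts the contrast by q × D when control has no matching loss. With 50 per arm, SE = sqrt(DE/(50(1 − q)) + 1/50), where DE is the design effect in the MTAR arm. DE = 1 for independent patients. With therapy groups of 6 (section 1: "in groups of 5 to 7 subjects per group"), DE = 1 + 5 × ICC, which is 1.25 and 1.50 at assumed ICCs of 0.05 and 0.10.

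| q | D | Bias (SD) | SE, DE = 1 | Bias/SE, DE = 1 | Bias/SE, DE = 1.25 and 1.50 |
|---|---|---|---|---|---|
| 10% | 0.2 | 0.02 | 0.205 | 0.10 | 0.09, 0.09 |
| 20% | 0.5 | 0.10 | 0.212 | 0.47 | 0.44, 0.42 |
| 30% | 0.8 | 0.24 | 0.220 | 1.09 | 1.02, 0.96 |

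The sign reverses if D does. With loss in both arms the bias is the difference of the two products: 0.3 × 0.8 − 0.2 × 0.5 = 0.14 SD. It is zero if D = 0 or if both arms have the same q and D.

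**4. Effect on the test.** A simulation with no true effect used 50 per arm, pre/post correlation 0.7, patients who did worse more likely to be dropped (latent correlation 0.5), and no clustering. Type I error was 0.052 with 30% loss in both arms, 0.110 with 30% against 10%, and 0.175 with 40% against 10%. These inputs are also assumed.

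**5. Precision.** This uses a two-sample t approximation, two-sided 5%, d = 2f = 0.66 and equal loss in both arms; it is not the planned ANOVA.

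| Analysed per arm | DE = 1 | DE = 1.25 | DE = 1.50 |
|---|---|---|---|
| 50 | 90.4% | 86.9% | 83.2% |
| 38 (24% lost) | 81.0% | 76.3% | 71.9% |

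The second row holds group size at 6. If loss shrinks groups to 6 × 0.76 = 4.6, the two clustered values are about 78% and 74%.

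**6. Calendar (minor and separate).** Section 4.3 spreads five sessions over five to seven weekdays in a row. From a weekday Day 4, five weekdays end on Day 8 (Monday start) or Day 10 (Tuesday to Friday start), six on Day 11, and seven on Day 12 (Monday to Thursday start) or Day 14 (Friday start). Table 4 ends the sequence on Day 10, and section 4.3 puts the post-test after the sequence. The end of the treatment phase, which bounds the drop rule, is therefore not fixed.

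**The case against.** The case for leaving the rule alone has real parts.

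- **Bias is not shown.** Correct. Every input in step 3 is assumed, most combinations give well under one standard error, and equal non-informative loss does no harm to validity. The stay criterion and section 5.7 also limit early loss. But an average stay of 7 to 10 days against a post-test on Days 8-10 leaves early discharge realistic.
- **The sample has slack.** With independent patients and a two-group effect of f = 0.33, 100 patients keep about 80% power up to roughly 25% loss. That stands for precision, less so with clustering, and it does nothing for bias.
- **Baseline data are kept.** Dropped and retained patients can be compared by arm on baseline ISMI and diagnosis, and assumption-based sensitivity analyses can be run. That stands, but neither reveals how the dropped patients changed.
- **A different model adds little.** With two time points, a patient with baseline only carries little information on change. This is right; the gain comes from collecting the post-tests.
- **The hypothesis in 3.2 speaks of completing the sequence.** Control has no sequence to complete, so MTAR completers against all controls is not the allocated comparison.
- **Phone post-tests tie mode and setting to discharge.** This is a genuine cost, carried into the fix.
- **Clustering and the calendar are side issues.** Agreed. Five weekday sessions on five consecutive weekdays fit Table 4; the mismatch arises only with six or seven weekdays.

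**Conclusion.** The concern holds. That the rule removes patients after allocation, stops their measurement and leaves a completers' comparison follows from sections 5.2, 3.4 and 5.8.2 with no outside assumption. The consequence is conditional: biased if loss differs by arm in amount or kind and is related to change in ISMI, less precise only if loss is equal and non-informative. Across the assumed range the bias is 0.02-0.24 SD of change in either direction, at most about one standard error. Loss of power is a comparable worry, so bias is not ranked above it. It must be fixed in advance because a post-test that was never collected cannot be recovered and its absence cannot be checked against observed outcomes. The calendar mismatch is minor and adds no weight.

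**What to change.** 1. **Replace the data-collection rule in 5.2.** Patients who are discharged early or miss sessions stay in data collection unless they withdraw consent. Collect their post-test ISMI in the planned window, by phone if discharged, and their 3-week ISMI.
2. **Record by arm** the sessions attended, the mode of administration, and the date and reason for any loss.
3. **State the analysis set in 5.8.2.** The primary analysis includes all allocated patients by allocated wing, with a model that keeps partial data and accounts for the therapy groups. Name the missing-data method.
4. **Define *noncompliant* and *completer* in advance** and report completers as a sensitivity analysis.
5. **Reconcile the calendar:** the anticipated-stay criterion, the span of weekdays in 4.3, Table 4, and the two post-test timings. State when the treatment phase ends for the purpose of data collection.

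The cost is protocol wording and some extra calls by existing research staff. Phone response will be incomplete; section 4.1.1 itself says "patient adherence to aftercare plans can be unpredictable". Mode of administration will be tied to discharge status, so it has to be recorded and considered when the result is read. The estimate may be diluted by patients who attended few sessions.
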